#### **Statistical Analysis Plan**

Protocol Title:	A Phase 1 Study of AMG 176 as Monotherapy and in Combination with Azacitidine in Higher-Risk Myelodysplastic Syndrome and Chronic Myelomonocytic Leukemia.		
Short Protocol Title:	Phase 1 Study of AMG 176 w Subjects with MDS/CMML	ith Azacitidine in	
Protocol Number:	20200392		
NCT Number:	Not available at the time of an	nendment	
Authors:			
Sponsor:	Amgen, Inc.		
	[name]		
SAP Date:	Document Version [	Date	
	Amendment 1 (v2.0)	10 May 2024	

Version Number	Date (DDMMMYYYY)	Summary of Changes, including rationale for changes	
Original (v1.0)	20OCT2021	Original Version	
Amendment 1 (v2.0)	10MAY2024	
 
CMML is added along with R/R MDS in the secondary objectives.
 
Secondary endpoint 'Evaluate the pharmacokinetics (PK) of the AMG 176 when administered as monotherapy' is added.
 
Overall response according to Uniform Response Criteria is now changed to overall response according to International Working Group (2006) -MDS/MPN Response criteria throughout the SAP except for objectives and endpoints.
 
	

Protocol Number: 20200392

Date: 10 May 2024 Page 2 of 33

•	The description for Part 1 changed
	from 'Dose Escalation/
	Determination of Maximum
	Tolerated Combination Dose
	(MTCD) and Recommended
	Phase 2 Dose (RP2D)' to 'Dose
	Escalation/Determination of Optimal
	Biological Dose (OBD) and
	Minimum Safe and Biologically
	Effective Dose (MSBED)

- Two dose levels in part 1 changed to three dose levels.
- The text of MTDC/RP2D definition is now replaced with 'The DLRT may change the dose/dosing scheduled based on emerging data. The OBD/MSBED is defined as the minimum safe and biologically effective combination dose with a probability of DLT lower than or close to a targeted toxicity probability of 0.2'
- In Part 2 the enrollment in newly diagnosed subjects is changed as 'subjects will not be enrolled into this cohort until all previous cohorts have been completed and the data reviewed by the FDA. Toxicity will be monitored for each cohort using a Bayesian approach proposed by Thall, Simon, and Estey (1995).'
- Prior distribution parameters are changed to beta (1,1) whereas initially it was beta (0.50, 1.50).
- The posterior probability that the incidence is greater than 30% is > 90% is changed to '20% is greater than 80%.
- The sample size changed from 110 subjects to 120 subjects and number of subjects in part 1 changed from 50 to 60
- BOR definition is updated as BOR is defined as the first response category achieved as responders and non-responders. Responders will include CR or PR, whereas

Protocol Number: 20200392

Date: 10 May 2024 Page 3 of 33

non-responders will include SD, PD, NE or NA.

 
Section 10- changes from protocol specified analysis is updated.
 

 
Section 9.1- Updated the general considerations.
 

 
Section 9.5.2- Updated to include listings for responder/non-responder.
 

Protocol Number: 20200392

Date: 10 May 2024

#### **List of Abbreviations**

Abbreviation	Explanation
ALP	alkaline phosphatase
ALT	alanine aminotransferase
ALT	alanine aminotransferase
AML	acute myeloid leukemia
ANC	absolute neutrophil count
AST	aspartate aminotransferase
ASTX727	Cedazuridine
AUC	area under the curve
BAK	pro-apoptotic effector proteins BCL2 homologous antagonist/killer
BAX	pro-apoptotic effector proteins BCL2-associated X
BCL2	B-cell lymphoma/leukemia 2
BCRP	breast cancer resistance protein
ВН3	pro-apoptotic BCL2 homology 3
BIM	BCL2-interacting mediator of cell death
BUN	blood urea nitrogen
CC-486	Azacitidine
CFR	U.S. Code of Federal Regulations
CIOMS	Council for International Organizations of Medical Sciences
CK-MB	creatine kinase-muscle/brain
CL	Clearance
C max	maximum concentration
CMML/CMMoL	chronic myelomonocytic leukemia
COVID-19	Coronavirus Disease 2019
CR	complete remission
CrCl	creatinine clearance
CRF	case report form
CRi	incomplete count recovery
CTCAE	Common Terminology Criteria for Adverse Events
CYP	cytochrome P450
DDI	drug-drug interaction
DILI	drug induced liver injury
DLRM	dose level review meeting
DLRT	dose level review team

Protocol Number: 20200392

Date: 10 May 2024 Page 7 of 33

DLT dose limiting toxicity
DOR duration of response
DR durable response
ECG Electrocardiogram
Echo Echocardiogram

ECOG PS Eastern Cooperative Oncology Group Performance Status

eCRF electronic case report form
EDC electronic data capture
EFS event-free survival

EOS end of study

EOT end of treatment

FAB French – American – British subtypes

FAS full analysis set

FDA Food and Drug Administration

FIH first in human

FSH follicle-stimulating hormone

GCP Good Clinical Practice

G-CSF granulocyte-colony stimulating factor

GLP good laboratory practices
GSO Global Safety Officer
HALS Houston Area Locations
HbcAb hepatitis B core antibody
HbsAb hepatitis B surface antibody
HbsAg hepatitis B surface antigen
HCVAb hepatitis C virus antibody

hERG human ether-à-go-go-related gene

Hgb Hemoglobin

HI hematologic improvement

HIPAA Health Insurance Portability and Accountability Act

HIV human immunodeficiency virus

HMA hypomethylating agent

HNSTD highest-non-severely-toxic dose

HR higher-risk

HSCT hematopoietic stem cell transplant

IB Investigator's Brochure

IC50 half-maximal inhibitory concentration

Protocol Number: 20200392

Date: 10 May 2024 Page 8 of 33

ICF informed consent form

ICH International Council for Harmonisation

ICJME International Committee of Medical Journal Editors

IEC Independent Ethics Committee

IND Investigational New Drug
INR international normalized ratio

IPSS International Prognostic Scoring System

IPSS-R Revised IPSS

IRB Institutional Review Board

IRT interactive response technology
ISS International Staging System

ITT intent-to-treat

IUD intrauterine device

IUS intrauterine hormonal-releasing system

IV Intravenous

Ki mean inhibitory constant

KM Kaplan-Meier

LDH lactate dehydrogenase

LVEF left ventricular ejection fraction
MAD maximum administered dose

MCL1 Myeloid Leukemia Cell 1

mCR marrow/morphologic complete remission

MDS myelodysplastic syndrome

MDSCs Myeloid Derived Suppressor Cells

MM Multiple Myeloma

MOA mechanism of action

MOLM acute monocytic leukemia (AML-M5a) cell lines

MOMP mitochondrial outer membrane permeabilization

MPN myeloproliferative neoplasm

MPN-SAF MPN Symptoms Assessment Form

MRD minimum residual disease

MRI magnetic resonance imaging

MSBED minimum safe and biologically effective dose

mTPI modified Toxicity Probability Interval

MUGA scan Multigated Acquisition scan
NCI National Cancer Institute

Protocol Number: 20200392

Date: 10 May 2024 Page 9 of 33

NCT National Clinical Trials

NE Not evaluable

NK cells natural killer cells

NT-pro BNP N-terminal prohormone of brain natriuretic peptide

NYHA New York Heart Association

OATP organic anion polypeptide transporters

OBD optimal biological dose
ORR overall response rate

OS overall survival

PBMC peripheral blood mononuclear cell

PCR polymerase chain reaction

PD progressive disease

PFS progression free survival

PI principal investigator
PK Pharmacokinetics

PLT Platelets

PR partial remission

PUMA p53-upregulated modulator of apoptosis

Q2W every 2 weeks

QD2 once daily for 2 consecutive days

QRS QRS interval is the interval between the Q wave and the S wave

in the heart's electrical cycle as measured by ECG; represents

the time it takes for the depolarization of the ventricles

QTc corrected QT interval

QTcF QT interval with Fridericia's correction

QW once weekly

R/R relapsed or refractory
RA refractory anemia

RAEB refractory anemia with excess blasts

RAEB-T refractory anemia with excess blasts in transformation

RARS refractory anemia with ringed sideroblasts

RBC red blood cell

SAP statistical analysis plan

SC Subcutaneous
SD stable disease

siRNA small interfering RNA

Protocol Number: 20200392

Date: 10 May 2024 Page 10 of 33

SOC standard of care

STD severely-toxic dose

t1/2 half-life

TBL total bilirubin

TI transfusion independence

TLS tumor lysis syndrome
TSS Total Symptom Score
TTNT time to next treatment
ULN upper limit of normal
UPM Unit Probability Mass
URL Upper Reference Limit

USPI United States Prescribing Information

Ven Venetoclax

WBC white blood cells

WHO World Health Organization

WHODRUG World Health Organization Drug

Protocol Number: 20200392

Date: 10 May 2024 Page 11 of 33

#### 1. Introduction

The purpose of this Statistical Analysis Plan (SAP) is to provide details of the statistical analyses that have been outlined within the **protocol superseding amendment 3** for study 20200392, AMG 176 dated **28 April 2022**. The scope of this plan includes the final analysis that is planned and will be executed by the Amgen Global Biostatistical Science department unless otherwise specified.

#### **Secondary**

Part 1A – QW Monotherapy (Dose Exploration)

Protocol Number: 20200392

Date: 10 May 2024 Page 12 of 33

Evaluate preliminary efficacy of AMG 176 QW when given as monotherapy in R/R MDS/CMML	Overall response according to the Uniform Response Criteria for MDS/MPN, Event-Free Survival (EFS), time to response, and Duration of Response (DOR)
Evaluate the pharmacokinetics (PK) of AMG 176 when administered as monotherapy	PK parameters for AMG 176 including, but not limited to, maximum observed concentration (C max ), area under the concentration-time curve (AUC), clearance (CL), and half-life (t 1/2 )
Part 1B – QW Combination Therapy (Dose Exp	loration)
Evaluate preliminary efficacy of AMG 176 QW in combination with azacitidine in R/R MDS/CMML	Overall response according to the Uniform Response Criteria for MDS/MPN, EFS, time to response, and DOR
Evaluate the PK of AMG 176 and azacitidine when administered in combination	PK parameters for AMG 176 and azacitidine including, but not limited to, C max , AUC, CL, and t 1/2
Part 2 – QW Combination Therapy (Dose E	Expansion)
Evaluate the preliminary efficacy of AMG 176 in combination with azacitidine in subjects with R/R HR-MDS/CMML in:	Time to transformation to Acute Myeloid Leukemia (AML)  Duration of Response (DOR)

 
HMA Failure, Venetoclax-Naïve
 
HMA Failure, Venetoclax-Exposed
 
To assess the preliminary efficacy of AMG 176 in combination with azacitidine in subjects with Newly Diagnosed MDS/CMML
 
	Overall Survival (OS)     Time to Next MDS Treatment (TTNT)     EFS
Evaluate the PK of AMG 176 and azacitidine when administered in combination	PK parameters for AMG 176 and azacitidine including, but not limited to, C max , AUC, CL, and t 1/2

#### 2.2 Hypotheses and/or Estimations

The clinical hypothesis is that at least 1 dose level of AMG 176 administered in combination with azacitidine will achieve acceptable safety and tolerability in subjects with HR-MDS. No formal statistical hypothesis will be tested.

#### 3. Study Overview

#### 3.1 Study Design

This study is a phase 1 clinical trial designed to assess the safety, tolerability, and efficacy of AMG 176 as monotherapy and in combination with the 7-day regimen of

Protocol Number: 20200392

Date: 10 May 2024 Page 13 of 33

azacitidine for the treatment of HR-MDS/CMML. Subjects will be treated with Intravenous (IV) AMG 176 and IV or Subcutaneous (SC) azacitidine. The study consists of two parts.

### Part 1 – Dose Escalation/Determination of Optimal Biological Dose (OBD) and Minimum Safe and Biologically Effective Dose (MSBED)

In Part 1, the modified Toxicity Probability Interval (mTPI) design will be applied for dose escalation.

Three dose levels of AMG 176 monotherapy will first be tested in Part 1A, and after the OBD or MSBED is found, three dose levels of AMG 176 in combination with azacitidine will be tested in Part 1B.

Each dose cohort will initially enroll 3 to 4 subjects and up to 10 subjects per cohort may be enrolled. After reviewing all available safety data, dose level recommendations (eg, escalation, de-escalation) will be made by the Dose Level Review Team (DLRT) using an mTPI model (Ji et al, 2010) based on all subjects that have been enrolled at the current dose. The DLRT may change the dose/dosing scheduled based on emerging data. The OBD/MSBED is defined as the minimum safe and biologically effective combination dose with a probability of DLT lower than or close to a targeted toxicity probability of 0.2.

Dose escalation is considered complete if one of the following rules is met:

- 1. The highest planned dose level is evaluated, OBD has not been defined, and no DLTs occur at any dose level. In this case, the Maximum Administered Dose (MAD) may be used for Part 2.
- 2. An OBD is identified.

Guidelines for dose level decisions can be found in Table 3-1. Details regarding the mTPI model are described in Appendix B.

Table 3-1. Guidelines for Dose Level Decisions in Part 1

	Number of DLTs		
No. of DLT-evaluable a subjects treated at current dose	Escalate	Stay at current dose	De-escalate b
3	0	1	≥ 2
6	0-1	-	≥ 2
9	0-1	2	≥ 3

Protocol Number: 20200392

Date: 10 May 2024 Page 14 of 33

	Number of DLTs		
No. of DLT-evaluable a subjects treated at current dose	Escalate	Stay at current dose	De-escalate b
10°	0-1	2-3	≥ 4

DLT = dose limiting toxicity.

#### Part 2 – Dose Expansion (Not Applicable, did not enroll)

Upon completion of Part 1 of the study, the dose expansion phase will begin at the **OBD/MSBED** and drug administration schedule with the intention of confirming the safety and tolerability and determining the efficacy of AMG 176 in combination with azacitidine in not only R/R HR- MDS/CMML, but also in frontline HR-MDS/CMML. An additional 60 subjects will be enrolled in Part 2 of the study as follows:

- HMA Failure Cohort: stratified by venetoclax exposure history
  - HMA Failure, venetoclax-Naïve (n = 20)
  - HMA Failure, venetoclax-Exposed (n = 20)
- Newly Diagnosed (n = 20) subjects will not be enrolled into this cohort until all previous cohorts have been completed and the data reviewed by the FDA.
   Toxicity will be monitored for each cohort using a Bayesian approach proposed by Thall, Simon, and Estey (1995).

The incidence of grade 3 or higher treatment-related non-hematological adverse events will be evaluated once every 5 subjects have had the chance to receive at least 1 cycle of treatment at the determined dose level for Part 2. Assuming a prior distribution of beta (1, 1), if the posterior probability that the incidence is greater than 20% is > 80% at these interim analyses, the study will stop early. The purpose of the safety interim analyses is to assess if the threshold for early termination has been reached. The stopping rules and operating characteristics are described in Protocol Table 3-2 and Table 3-3.

Table 3-2. Stopping Boundary for Each Cohort in Part 2

Number of subjects	Stop study if observing this number of subjects with grade 3 or higher treatment-related non-hematological adverse event
5 ~ 6	≥ 2

<sup>a A subject is considered DLT-evaluable if he/she experienced a DLT during the DLT evaluation period; or if he/she received 75% of the planned doses of AMG 176 and 100% of the planned doses of azacitidine and completed the DLT evaluation period.

<sup>b De-escalate guideline applies only when current dose level and enrollment is allowed to a lower dose level.

<sup>c The maximum number of evaluable subjects at one dose level is 10.

Protocol Number: 20200392

Date: 10 May 2024 Page 15 of 33

7 ~ 10	≥ 3
11 ~ 14	≥ 4
15 ~ 19	≥ 5
20	Completes

Table 3-3. Operating Characteristics in Part 2

True grade 3 or higher treatment-related non-hematological adverse event rate	Probability of early stopping
0.10	15%
0.15	32%
0.20	51%
0.25	69%
0.30	82%

#### 3.2 Sample Size

It is anticipated that up to 120 subjects will be enrolled in the study, with up to 60 subjects in Part 1 and 60 subjects in Part 2.

For each part, the sample size is based on practical considerations **and it is consistent** with conventional oncology studies with the objective to identify the OBD/MSBED.

#### 3.3 Adaptive Design

NA

#### 4. Covariates and Subgroups

#### 4.1 Planned Covariates

There are no planned covariates in this study.

#### 4.2 Subgroups

There are no planned subgroups in this study.

#### 5. Definitions

#### **Age at Enrollment:**

Age at Enrollment: Subject age at enrollment will be collected in [years] in the clinical database

Protocol Number: 20200392

Date: 10 May 2024 Page 16 of 33

#### Baseline:

Unless otherwise specified, baseline will be defined as the last assessment with nonmissing value before the first dose of investigational product (AMG 176).

#### **Baseline and Post-Baseline ECG Values in Triplicate:**

The baseline ECG is defined as the mean of all pre-dose assessments, the mean of values in a triplicate should be calculated before taking the mean of the triplicate averages.

For all post-baseline ECG, the mean value for measurements taken at the same assessment will be calculated and used in the analysis.

When an ECG is missing within a triplicate, all available data will be averaged for that time point.

#### **Bazett-corrected QT Interval (QTcB):**

The Bazett correction will be calculated from the investigator reported QT (msec) and RR interval (msec): QTcB=QT/(RR/1000)1/2

#### Best Overall Response (BOR):

BOR for a subject is the best observed post-baseline disease response based on investigator assessment.

BOR is defined as the first response category achieved as responders and non-responders. Responders will include CR or PR, whereas non-responders will include SD, PD, NE or NA.

Response criteria to be used for MDS/**MPN** are International Working Group (**IWG**)-**MDS** Response Criteria (2006).

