#### 9. Statistical Methods of Analysis

#### 9.1 General Considerations

Descriptive statistics on required continuous data like Troponin I and Troponin T will include means, medians, standard deviations, first and third quartiles and ranges.

When data are summarized by time, the values recorded against the scheduled time points listed in the protocol will be used. When assessing minimum/maximum increases or decreases over the study, all assessments, including unscheduled assessments will be used.

No formal statistical analysis will be performed for the study and listings will be provided.

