## 9.5.2 Analyses of Secondary Efficacy Endpoint(s)/Estimand(s) The listing of responder/non-responder will be provided for Part 1A- QW Monotherapy (Dose Exploration) subjects.

#### 9.5.3 Analyses of Exploratory Efficacy Endpoint(s)

NA

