#### 14. Appendices

#### **Appendix A. Code Fragments**

The ORR and its 95% CI can be calculated in SAS using PROC FREQ. The sample code is provided below, where RESP is the status of response (eg., 1=responder, 2=non-responder). The CI using the exact method can be found in the OUT data labeled as 'Exact Conf Limits'.

proc freq data=TEST; tables RESP / binomial alpha=0.05; ods output Binomial=OUT;

Protocol Number: 20200392

Date: 10 May 2024 Page 28 of 33

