# Appendix E. MDS Diagnostic and Response Criteria Proposed modified International Working Group response criteria for altering natural history of MDS

Category	Response criteria (responses must last at least 4 wk)					
Complete remission	Bone marrow: ≤ 5% myeloblasts with normal maturation of all cell lines*					
	Persistent dysplasia will be noted*†					
	Peripheral blood‡					
	Hgb ≥ 11 g/dL					
	Platelets $\ge 100 \times 10^9 / L$					
	Neutrophils ≥ $1.0 \times 10^9/L$ †					
	Blasts 0%					
Partial remission	All CR criteria if abnormal before treatment except:					
	Bone marrow blasts decreased by $\geq 50\%$ over pretreatment but still > $5\%$					
	Cellularity and morphology not relevant					
Marrow CR†	Bone marrow: ≤ 5% myeloblasts and decrease by ≥ 50% over pretreatment					
	Peripheral blood: if HI responses, they will be noted in addition to marrow CR†					
Stable disease	Failure to achieve at least PR, but no evidence of progression for > 8 wks					
Failure	Death during treatment or disease progression characterized by worsening of cytopenias, increase in percentage of bone marrow blasts, or progression to a more advanced MDS FAB subtype than pretreatment					
Relapse after CR or PR	At least 1 of the following:					
	Return to pretreatment bone marrow blast percentage					
	Decrement of ≥ 50% from maximum remission/response levels in granulocytes or platelets					
	Reduction in Hgb concentration by $\geq 1.5$ g/dL or transfusion dependence					
Cytogenetic	Complete					
	Disappearance of the chromosomal abnormality without appearance of new ones					
	Partial					
	At least 50% reduction of the chromosomal abnormality					
Disease progression	For patients with:					
	Less than 5% blasts: ≥ 50% increase in blasts to > 5% blasts					
1 2 A	5%-10% blasts: ≥ 50% increase to > 10% blasts					
	10%-20% blasts: ≥ 50% increase to > 20% blasts					
	20%-30% blasts: ≥ 50% increase to > 30% blasts					
	Any of the following:					
	At least 50% decrement from maximum remission/response in granulocytes or platelets					
	Reduction in Hgb by $\geq 2$ g/dL					
	Transfusion dependence

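### SAP Section 5 defines best overall response both as the best and as the first category, with no precedence; taken literally, the second rule would list a late CR or PR as a non-responder (minor)

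*SAP*

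**What the plan says.** The BOR entry in SAP Section 5 opens with "BOR for a subject is the best observed post-baseline disease response based on investigator assessment". The next sentence reads "BOR is defined as the first response category achieved as responders and non-responders", and the one after it fixes the two classes: "Responders will include CR or PR, whereas non-responders will include SD, PD, NE or NA". The entry then names the IWG 2006 criteria, which are reproduced in SAP Appendix E under the column heading "Response criteria (responses must last at least 4 wk".

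The SAP's summary of changes for Amendment 1 records the addition: "BOR definition is updated as BOR is defined as the first response category achieved as responders and non-responders". That entry has the same wording as the current text. It shows when the second rule came in, while the sentence about the best response stayed beside it.

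On outputs, SAP Section 9.1 states "No formal statistical analysis will be performed for the study and listings will be provided". Section 9.5.2 keeps one efficacy output: "The listing of responder/non-responder will be provided for Part 1A- QW Monotherapy (Dose Exploration) subjects".

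**The concern.** Best and first are different derivation rules, and both stand in the operative text. The SAP says which governs neither in Section 5 nor in Section 9.5.2, Section 10, Appendix A or Appendix E. The sentence on first category covers non-responders as well as responders, and the non-responder class includes NE and NA. A programmer following it literally could therefore fix a subject's status at the first assessment, so that a later CR or PR would not count.

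With the response tables dropped after early termination, the Part 1A listing is all that a reader will see on response. A delayed responder shown there as a non-responder would have no table or estimate elsewhere to correct the picture.

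**Working it through.** No figure in the plan needs reproducing. The check applies each possible rule to the same response sequences.

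**Inputs.** The six categories named in the SAP Section 5 BOR entry: CR and PR (responder); SD, PD, NE and NA (non-responder). Any CR or PR is taken as already meeting the 4-week duration in Appendix E. No response rate or timing is assumed.

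**Examples.**

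| Sequence | Best response | First assessed category | First CR or PR reached |
|---|---|---|---|
| SD then CR | responder (CR) | non-responder (SD) | responder (CR) |
| NE then PR | responder (PR) | non-responder (NE) | responder (PR) |
| PD then PR | responder (PR) | non-responder (PD) | responder (PR) |
| PR then CR | responder (CR) | responder (PR) | responder (PR) |
| CR then PD | responder (CR) | responder (CR) | responder (CR) |
| SD then PD | non-responder | non-responder | non-responder |

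**Count over all ordered pairs.**

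- Sequences: 6 × 6 = 36.
- Responder under the best-response rule (at least one CR or PR): 36 − 4 × 4 = 20.
- Responder under the first-assessed rule (first of the pair is CR or PR): 2 × 6 = 12.
- Flag differs: 20 − 12 = 8. These are the pairs with SD, PD, NE or NA first and CR or PR second, 4 × 2 = 8. The reverse change cannot occur, because a CR or PR at the first assessment also counts under the best-response rule.
- Setting aside sequences that start with PD: 3 × 2 = 6.
- If the sentence means the first CR or PR reached, the flag differs in 0 of 36 and the CR-versus-PR label in 1 of 36 (PR then CR).
- If category means only the two-way class, as the coding in SAP Appendix A suggests ("RESP is the status of response (eg., 1=responder, 2=non-responder"), that label difference also disappears. The first-assessed rule still changes the flag in 8.

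**Timing.** Protocol Section 1.3 (schedule footnote on cytomorphology) places the first scheduled post-baseline marrow before dosing on cycle 2 day 1, the next on cycle 3 day 1, and later ones before every other cycle. With 28-day cycles and no delay, the first falls 28 / 7 = 4 weeks after the first dose. Table 1-2 also carries an every-cycle entry matching the overall disease response row of Table 1-4, and Protocol Section 8.3.1 allows additional marrows. Appendix E requires more than 8 weeks without progression for SD. At the first scheduled marrow, a subject not in CR or PR therefore cannot yet meet SD and could be recorded as NE or NA. A rule fixed at that visit would ignore any later response.

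**The case against.** The strongest reply is that the literal reading is not the natural one. The term being defined is best overall response, the opening sentence says so, and CR or PR is something a subject achieves while NE or NA is not. Read together, the opening sentence selects the response and the next sorts it into two classes. Appendix E points the same way: a status fixed at about week 4 can apply neither its 4-week duration nor its 8-week SD criterion without later data. This stands as an argument about intent. It does not alter the wording, which puts both classes, NE and NA included, under the word first.

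A second reply is that the listing may not depend on this sentence. Section 9.5.2 does not mention BOR, the definition refers to investigator assessment, and SAP Appendix C lists a form for best overall response and progression, so the status may be recorded directly. This also stands in part. The link to the listing is an inference, although Section 5 is the only place where the SAP defines the responder classes. The form's content cannot be seen.

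A third reply is that little turns on it. This is right and sets the severity.

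**Conclusion.** The SAP holds two conflicting current rules for BOR and no precedence between them. That is a defect in a stated definition rather than a missing detail. Its size is minor. Only the first-assessed reading changes a responder flag, it does so in one direction only, and it is probably not what was meant. The effect is confined to one subject-level listing and rests on the assumption that the listing is derived from Section 5.

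A reader might go further in three ways that the documents do not support.

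- That subjects have been misclassified. The documents give neither the number enrolled nor any response timing, so the number affected is unknown and may be zero.
- That a response rate or its confidence interval is biased. Appendix A still holds code for both, but Sections 9.1, 9.5.1 and 10 plan no such analysis, so no estimate, interval or test changes.
- That marrow CR and cytogenetic responses are thereby settled as non-responders, or wrongly left out. Section 5 names only CR or PR. The ORR endpoint that counts marrow CR and cytogenetic response (Protocol Section 3, SAP Section 2.1) belongs to Part 2, which did not enroll, and does not govern the Part 1A listing.

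**What to change.** In SAP Section 5, delete the wording about the first category and state one rule: BOR is the best category over all post-baseline assessments under Appendix E, including its 4-week duration, and a responder is a subject whose BOR is CR or PR. If the date of first CR or PR is wanted, list it as a separate variable. Say in Section 9.5.2 that the listing uses this BOR.

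Do not relabel marrow CR or cytogenetic responses as part of this change. If they are shown, use separate flags, with a note that the Part 2 ORR endpoint counts them while the BOR definition names only CR or PR.

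The cost is one sentence in Section 5, a cross-reference in Section 9.5.2 and, at most, a few optional columns in one listing. No new data are needed for the BOR rule or the date: the forms for disease response and for best overall response and progression are already listed in SAP Appendix C.
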